2.0 Definitions related of safety

- 2.1 Mental health safety symptom severity, deterioration is assessed using the PCL-5 selfreport screening questionnaire (39, 67, 68) completed by the participant at the beginning of every therapy session until discharge. Any existing or emergent safeguarding and or vulnerable adult concern will be assessed and monitored at each session with proportionate action taken in accordance with legislative reporting requirements.
- 2.2 Mental health safety is assessed using the PCL-5 self-report screening questionnaire completed by the participant at the following time points following discharge; 6 weeks post randomisation which is likely to be post discharge in the RTM group and during therapy in the TF-CBT group; 12 weeks post randomisation; 20 weeks post randomisation and 52 weeks post randomisation.
 - 2.2.1 The named researcher will review all incoming follow up PCL-5 scores within 72 hrs of receipt.
- 2.3 PTSD Adverse Events are defined as a ≥10 point rise in the self-report PCL-5 since the previous therapy session or a 15 point rise from baseline or the maximum score of 80 being reached and/or relapse into alcohol and/or substance misuse at a hazardous level which integrated with the clinical judgement of the treating therapist will determine the action taken
- 2.4 PTSD Serious Adverse Events are defined as hospital admission for mental ill-health, selfharm, suicide and attempted or completed suicide.

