3.9 Confidentiality and anonymity

Each participant's personal details will be linked to their study identifier in an excel spreadsheet that five members of the research team will have access to, ([name] and an Inspire named individual). Responsibility for managing this database will be held with the KCL researcher and the database will be held on a secure KCL server. All data collection and recording will be GDPR compliant and conform with Inspire's standardised risk assessment, escalation, management and safeguarding policies and procedures. We are aware of the particularly sensitive nature of mental health and military veteran status in this population.

Video-recordings of each therapy session, or at a minimum audio recording, will be undertaken to determine therapist competence, and consequently participant safety. If the therapy is taking place online, the therapist and participant will decide which video conferencing interface to use and with the participant's permission we will record the session using the online recording facilities within each interface. This is in adherence with Inspire's current governance regime. Once the session is completed the recording will be encrypted, password protected and saved to a secure computer folder. If the therapy is being delivered face-to-face we will use a video camera and stand with an SD card. The video is uploaded via the SD card onto to a secure and encrypted memory stick. Both the online and face-to-face recordings will be shared in person or via video-meeting via Zoom with their research clinical supervisor/s and up to four therapy peers during fortnightly group and individual clinical supervisions. Zoom is a web and video conferencing platform that is suitable for use in healthcare and is compliant with EU's GDPR and US's Health Insurance Portability and Accountability (HIPAA) [https://zoom.us/privacy]. The video-recording will not leave the therapist's possession and will not be shared digitally. The online recording or the SD card will be wiped clean following each clinical supervision. Participants will be able to specifically opt out of this on the consent form and consent to audio as an alternative. It is not safe to expose participants to experimental psychological interventions without objective evidence of what has been delivered. Our procedures have been developed to balance participant safety with confidentiality and anonymity.

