3.13 Data Collection

Socio-demographic and medical history variables will be obtained from Inspire's clinical records following the completion of eligibility, informed consent procedures, baseline data collection and diagnostic confirmation assessment. Each participant's demographic and medical history data will be entered onto the study database hosted on the King's College London secure server. Data will be entered by a researcher or a trained Inspire administrator and a participant identification number will be generated.

Feasibility, acceptability, cost and safety outcomes will be collected by the QUB researcher by monitoring when and why participants drop out of either intervention or the research study. Costs of therapy data will be recorded by both TF-CBT and RTM therapists based on £75.00 per session for the number, duration and location of therapy sessions per participant and collated by the researcher. Therapy location data will be collected to incorporate therapist travel into the delivery costs. The independent clinical psychologist will inform the researcher when any participant makes contact, the frequency and duration of these contacts and the outcome.

Health and Social Care Outcomes will be collected via a series of validated questionnaires. Following completion of informed consent procedures and prior to randomisation, baseline data will be

collected from the participant with follow up taking place at 6, 12, 20 and 52 weeks post randomisation. Data collection will be undertaken either in person (aligned to a therapy appointment where they coincide), over the telephone (with paper copies having been sent via post in advance), or electronically (by secure web data collection software or email). The participant can choose their preferred method at each follow up point. Paper questionnaires, with participant identifiers, will be scanned and sent via encrypted email from Queen's University Belfast to the King's College London Trial Manager. Electronically completed surveys will be sent by encrypted email in the same way. Data will be entered into a project specific eCRF database supported by KCTU and hosted on the KCTU server. Follow up data will be acceptable if it is completed/collected 10 working days either side of the official follow-up date at 6, 12 and 20 weeks and within one calendar month at 52 week follow up. Data arriving outside of these time period will be classed as missing for the purpose of analysis.

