3.15.4 Data management

A web based electronic data capture (EDC) system has been designed, using the InferMed Macro 4 system. The EDC will be created in collaboration with the trial analyst/s and the CI and maintained by the King's Clinical Trials Unit for the duration of the project. It will be hosted on a dedicated secure server within KCL.

The CI or delegate will request usernames and passwords from the KCTU. Database access will be strictly restricted through user-specific passwords to the authorised research team members. It is a legal requirement that passwords to the EDC are not shared, and that only those authorised to access the system are allowed to do so. If new staff members join the study, a user-specific username and password must be requested via the CI or delegate (e.g. Trial Manager) from the KCTU team and a request for access to be revoked must be requested when staff members leave the project. Study site staff experiencing issues with system access or functionality should contact the CI or delegate (e.g. Trial Manager) in the first instance.

No identifiable data beyond participant initials and age at consent will be entered on the EDC or transferred to the KCTU. No data will be entered onto the EDC system unless a participant has signed a consent form to participate in the trial. Source data will be entered by a researcher or Inspire nominated individual, typically within eight days of data collection by authorised staff onto the EDC by going to www.ctu.co.uk and clicking the link to access the MACRO 4 EDC system. A full audit trial of data entry and any subsequent changes to entered data will be automatically date and time stamped, alongside information about the user making the entry/changes within the system.

The CI team will undertake appropriate reviews of the entered data, in consultation with the project analyst, for the purpose of data cleaning and will request amendments as required.

At the end of the trial, the site PI will review all the data for each participant and provide electronic sign-off to verify that all the data are complete and correct. At this point, all data can be formally locked for analysis.

Upon request, KCTU will provide a copy of the final exported dataset to the CI in .csv format and the CI will onward distribute as appropriate.

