1.0 Lines of responsibility and accountability

- 1.1 From the point at which a potential participant is handed over to Inspire for eligibility assessment through to the point of discharge, Inspire have responsibility and clinical governance accountability for the participant's mental health and wellbeing and including their own safety and where relevant the safety of others and including the safeguarding of children and vulnerable adults.
- 1.2 From the point of discharge from Inspire therapy to the point of 52 week follow, up or withdrawal from the trial, the participant's GP holds responsibility and accountability for the participant's mental health and wellbeing and this includes their safety.
- 1.3 Participant safety will be a standing agenda item on every fortnightly King's- QUB research team meeting.
- 1.4 Data Monitoring and Ethics Committee (DMEC) will meet four times during the trial comprising three trauma experts, a veteran welfare expert and an independent statistician. The DMEC terms of reference will operate according to the King's Clinical Trials Unit Standard Operating Procedures. The research team will report any participant safety issues to the DMEC within 48 hrs of each fortnightly King's and Queen's meeting.

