4.0 Care escalation procedures in the case of adverse event

- 4.1 If at point of referral or during the course of treatment, Inspire therapists become concerned about the welfare of any participant or immediate family member they will escalate their concerns through Inspire's standardised risk assessment, escalation, management and safeguarding policies and procedures. Where necessary they will contact the participant's GP to mobilise referral to crisis response, NHS primary or secondary care. Likewise, if a safeguarding and vulnerable adults concern is identified this will be escalated, acted on and reported to the relevant statutory body safeguarding team.
 - 4.1.1 The PCL- 5 along with Core-10 will be completed at each therapy session. If ≥10 point rise in PCL-5 score occurs since the previous therapy session, or 15 point rise from baseline, or the maximum score of 80 is recorded on the PCL-5 alongside an escalation in risk "flagged" using CORE-10, they will use their clinical judgement to assess whether escalation is appropriate.
 - 4.1.2 Any ≥10 point rise in PCL-5 score that occurs since the previous therapy session, or 15 point rise from baseline, or the maximum score of 80 is recorded on the PCL-5, will be detected by the unblinded member of the research team who will inform the DMEC chair within 3 working days.
- 4.2 If a participant's PCL-5 score rises by ≥10 points from the previous follow up, or 15 point rise from baseline, or the maximum score of 80 is recorded on the PCL5, the unblinded researcher will make contact with the participant within six hours of noting the rise in score and encourage them to contact their GP and/or their case worker. They will advise the participant that the researcher will need to contact the participant's case worker (or GP if no case worker) to alert them to the rise in PTSD symptoms.

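### After discharge, Appendix 1 reviews and escalates PCL-5 scores only; the PHQ-9 in the same follow-up booklet has no safety review, deadline or trigger

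*Protocol*

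**What the plan says.** Appendix 1 opens by describing itself as the safety protocol for all participants throughout the trial. Responsibility changes hands at discharge. Inspire is accountable until then (1.1); afterwards "the participant's GP holds responsibility and accountability for the participant's mental health and wellbeing and this includes their safety" (1.2).

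During therapy two scales are in use: "The PCL- 5 along with Core-10 will be completed at each therapy session" (4.1.1). A CORE-10 risk flag is read alongside the PCL-5 thresholds, and the therapist applies clinical judgement.

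For follow-up, section 2.2 names the PCL-5 as the measure of mental health safety at weeks 6, 12, 20 and 52. It describes the first of these as "6 weeks post randomisation which is likely to be post discharge in the RTM group and during therapy in the TF-CBT group". Section 2.2.1 sets the check: "The named researcher will review all incoming follow up PCL-5 scores within 72 hrs of receipt". Section 4.2 sets the response. If the PCL-5 has risen by at least 10 since the previous follow-up, has risen by 15 from baseline, or stands at 80, "the unblinded researcher will make contact with the participant within six hours of noting the rise in score". The participant is urged to contact the GP or case worker, and the researcher alerts the case worker, or the GP if there is none.

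The PHQ-9 is described in section 3.12.3.4 as nine items, one for each mood-related DSM-IV criterion, scored 0 to 3. In Appendix 5 (row 10) it comes from the same follow-up booklet at the same four time points. The only roles given there are for data entry.

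**The concern.** The score-based safety rules after discharge rest on one PTSD scale and, short of the maximum score, on change in that scale. A participant whose PTSD score is high but steady, or is improving, meets none of them, whatever the depression questionnaire in the same envelope or email shows.

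The plan takes suicide risk seriously. Section 2.4 counts self-harm and attempted or completed suicide as serious adverse events. Appendix 4 (Outcome 3) expects the safety protocol to deal with suicide and attempted suicide over the 20-week follow-up. Section 3.13 adds to the exposure: follow-up may be in person, by telephone or electronic, and "The participant can choose their preferred method at each follow up point". A form can therefore arrive with no member of staff present when it was completed.

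At stake is a written warning sign that the trial holds and that no rule obliges anyone to read for safety. The GP, who is by then accountable, cannot act on an answer that nobody has to forward.

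**Working it through.** No power or error-rate calculation applies. The check sets the rules for the two scales side by side and then asks which follow-up forms fall after discharge.

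**1. Rules for follow-up scores after discharge**

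| Element | PCL-5 | PHQ-9 |
|---|---|---|
| Person assigned to review for safety | Named researcher (2.2.1) | None |
| Review deadline | 72 hours from receipt (2.2.1) | None |
| Trigger | Rise of at least 10 from previous follow-up, 15-point rise from baseline, or 80 (4.2) | None |
| Action | Contact within six hours; case-worker or GP alert (4.2) | None |
| Data-entry role | Yes (Appendix 5, row 6) | Yes (Appendix 5, row 10) |

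The PCL-5 has four of the four safety elements and the PHQ-9 has zero of four.

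**2. How far the PCL-5 can move without a rule applying.** It is a sum of item scores from 0 to 80 (3.12.3.1), so it takes whole-number values. No rule in 4.2 is met if all three of these hold:
- rise since previous follow-up no more than 10 − 1 = 9;
- rise from baseline no more than 15 − 1 = 14;
- score no more than 80 − 1 = 79.

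Within that region any PHQ-9 response, including an endorsed suicidal-thoughts item if the form has one, meets no score-based rule.

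**3. Which forms fall after discharge.** Therapy is to start within two weeks of randomisation (3.10) and is weekly (3.11.1, 3.11.2). With a start at week s, where s is 0 to 2, session k falls at week s + (k − 1):
- RTM, up to 5 sessions: last session at weeks 4 to 6.
- TF-CBT, 12 sessions as laid out for simple PTSD: weeks 11 to 13.
- TF-CBT, up to 18 sessions: weeks 17 to 19.

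On this timetable weeks 20 and 52 are post-discharge in both arms, week 12 is post-discharge for RTM and may be for TF-CBT, and week 6 is uncertain for RTM, as 2.2 itself says. Anyone who leaves therapy early but stays in the research reaches this state sooner. During therapy the CORE-10 and a therapist are also present, so the gap is clearest after discharge.

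**4. Do other post-discharge provisions supply a PHQ-9 check?**
- GP accountability (1.2): no rule sends the answer to the GP.
- Safety agenda item and DMEC reporting (1.3, 1.4): these operate once the team has noticed an issue.
- Contact card and logging of self-reported contacts (3.1, 3.1.2): they depend on the participant making contact.
- Independent psychologist line (3.2, 3.3): RTM only, and started by the participant or family.
- Questionnaire 8 feeding the adverse events log (Appendix 5, row 16): not the PHQ-9.
- Investigation of serious adverse events (5.2): starts after the event.
- Section 3.9: data collection will "conform with Inspire's standardised risk assessment, escalation, management and safeguarding policies and procedures". This is general, names no scale and gives no timing.

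None requires anyone to look at a PHQ-9 answer.

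**The case against.** The strongest objection is that the harm depends on an item the protocol never describes. Section 3.12.3.4 says only that nine mood-related criteria are scored. This stands as a limit: the suicidal-thoughts item is an assumption about the standard form. Without it, the PHQ-9 would still be an unreviewed depression score, but the proposed trigger would need a different definition.

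The second objection is that the safety plan is layered. Section 1.4 obliges the team to report any participant safety issue to the DMEC within 48 hours of each fortnightly meeting, and that is not confined to the PCL-5. Section 3.9 brings in Inspire's policies, which are not shown and may cover part of this. So it would be wrong to say that no duty exists. What stands is that these duties begin once somebody has noticed the answer. Moreover, 5.2 expressly carries Inspire's procedures past discharge for serious adverse events, and no equivalent sentence covers warning signs.

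A reader might also infer three stronger things that the document does not support.
- That a warning could routinely lie unread for eight days. Section 3.15.4 says data are entered "typically within eight days of data collection by authorised staff", but that is a database-entry time, not a reading time. The PCL-5 in the same booklet is due for review within 72 hours of receipt, so someone should be handling the booklet well before then.
- That only a recent suicide attempt keeps a high-risk veteran out. Exclusions 3 and 9 in 3.5.2 also allow exclusion for severe comorbidity or when other symptoms take precedence, and the psychologists apply Inspire's risk assessment at eligibility (Appendix 1, 6.1).
- That the problem can be sized by totalling post-discharge forms. Such a total depends on the number of TF-CBT sessions, on early drop-outs and on how attrition is spread. It would also mix attended with unattended completion and say nothing about how many forms carry a warning.

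**Conclusion.** The point holds, and the protocol should be changed. After discharge, the explicit score-based safety rules in Appendix 1 cover the PCL-5 alone, and the CORE-10 flag used in therapy is not replaced. A PHQ-9 warning with a PCL-5 inside the limits in step 2 of the check meets none of those rules. This goes beyond missing detail: Appendix 1 fixes the post-discharge rule, and fixes it too narrowly for the serious adverse events it defines in 2.4.

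The size is qualitative: zero of four safety elements for a questionnaire returned at four follow-ups. The number of participants who would endorse such an answer is not known from the document and is not estimated. The conclusion assumes the standard PHQ-9 with its suicidal-thoughts item, and that Inspire's unseen policies do not already set a check on follow-up forms received after discharge. Confidence is medium for those two reasons. It does not follow that participants are unprotected after discharge, only that no rule requires this information to be looked at.

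**What to change.** Amend Appendix 1 as follows.
- **2.2.1:** the named researcher checks the PHQ-9 suicidal-thoughts item at the same review as the PCL-5, within 72 hours of receipt at the latest and sooner where feasible.
- **4.2:** an endorsed answer on that item becomes a further trigger for the existing six-hour participant contact and case-worker or GP alert. The exact cut-off is for the clinical team to set.
- **Handover:** a blinded researcher who sees such an answer passes it at once to the unblinded researcher, who acts under 4.2. This is needed because Appendix 5 lists blinded as well as unblinded staff for PHQ-9 entry, while 4.2 gives the action to the unblinded researcher.
- **Inspire policies:** one sentence stating how the policies cited in 3.9 apply to forms received after discharge.

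The cost is a few sentences and one more item to read in a booklet already in hand, with no new instrument. There will be some extra contact calls and GP alerts, more of them if the cut-off is low. The two research posts are 60% (3.15.1), so the team should confirm that the added calls fit; keeping 72 hours as the outer limit avoids a new deadline. The change does not shorten the intervals between forms, the longest being 52 − 20 = 32 weeks.

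### Appendix 1 escalates a PCL-5 rise of 10 or more points between follow-ups (4.2), but definition 2.3 does not count that rise as an adverse event, so the adverse-event log can be incomplete after discharge

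*Protocol*

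**What the plan says.** Protocol Appendix 1, item 2.3, defines a non-serious adverse event as a PCL-5 rise of at least 10 points "since the previous therapy session or a 15 point rise from baseline or the maximum score of 80 being reached", and/or relapse into hazardous alcohol or substance misuse. No other item defines a non-serious event.

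Item 2.2 makes the PCL-5 the safety measure after discharge, at 6, 12, 20 and 52 weeks. It describes the first of these as "6 weeks post randomisation which is likely to be post discharge in the RTM group and during therapy in the TF-CBT group".

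Section 4.0 is headed "Care escalation procedures in the case of adverse event". Item 4.1 covers the therapy phase ("If at point of referral or during the course of treatment, Inspire therapists become concerned about the welfare of any participant"), and 4.1.2 repeats the triggers of 2.3. Item 4.2 covers follow-up. It acts when a participant's "PCL-5 score rises by ≥10 points from the previous follow up, or 15 point rise from baseline", or when the score is 80.

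Appendix 4, Outcome 3, asks for a log of every adverse event and for events to be contained over the 20-week follow-up. In Appendix 5, row 16 (adverse events log), the comment on follow-up names the participant through Questionnaire 8, the GP and the independent clinical psychologist. It does not name the PCL-5 form.

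**The concern.** Two of the three PCL-5 triggers, 15 points above baseline and a score of 80, are the same in 2.3 and 4.2. The third is not: 2.3 compares with the previous therapy session and 4.2 with the previous follow-up. The protocol therefore runs its adverse-event procedure for some scores that its own definition does not call adverse events.

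The cases affected are participants who improve and then lose ground after discharge. During therapy the 10-point rule has no baseline floor, so a partial loss of gain between two sessions is an adverse event. The same loss between two follow-ups is not, and no reason is given.

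At stake is the adverse-event log. Objective 3 (understanding the safety risks), research question f (how the safety protocol detects and limits adverse events) and Appendix 4, Outcome 3, all draw on it. Staff completing it would have to choose between the heading over 4.2 and the definition in 2.3.

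**Working it through.** The protocol gives no adverse-event rate, so there is no figure to reproduce. The check compares the two rules on the PCL-5 range of 0 to 80 (section 3.12.3.1). All example scores are assumptions.

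Let B = baseline, L = last therapy session, F = previous follow-up and X = current follow-up score, with no alcohol or substance relapse. Put D = B − F and E = L − F.

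**Step 1: the rules after discharge.**
- 4.2 is met if X − F ≥ 10, or X − B ≥ 15, or X = 80.
- 2.3, read literally (no therapy session to compare with), is met if X − B ≥ 15 or X = 80.
- 2.3, read with the last session held as comparator, is also met if X − L ≥ 10.

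**Step 2: literal reading.** The gap is F + 10 ≤ X ≤ min(B + 14, 79). Where the ceiling of 79 does not bind (B ≤ 65), this means rises of 10 to D + 14 points. With B = 50:

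| D | Rises that meet 4.2 but not 2.3 |
|---|---|
| 0 | 10–14 |
| 10 | 10–24 |
| 30 | 10–44 |
| −4 | 10 only |
| −5 | none |

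For D = 30, rises of 10–29 leave the participant still below baseline, and rises of 31–44 put them 1–14 points above it.

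**Step 3: last session as comparator.** The gap becomes F + 10 ≤ X ≤ min(B + 14, L + 9, 79), that is, rises of 10 to min(D + 14, E + 9). With B = 50 and F = 20:

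| E | Rises that meet 4.2 but not 2.3 |
|---|---|
| 0 | none |
| 1 | 10 only |
| 5 | 10–14 |
| 10 | 10–19 |

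The gap is empty unless the previous follow-up score is below the last-session score. For two follow-ups that both fall after discharge, this means the participant improved further after therapy ended.

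**Step 4: a case in the gap on both readings.** B = 50, L = 30, week 12 = 20, week 20 = 35.
- X − F = 35 − 20 = 15, at least 10: escalated under 4.2.
- X − L = 35 − 30 = 5, below 10.
- X − B = 35 − 50 = −15, below 15, and 35 is below 80.
- Not an adverse event under 2.3 on either reading.

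**Step 5: the first follow-up.** Week 6 is the first follow-up, so a participant discharged before it has no earlier follow-up for the 10-point rule in 4.2. By 2.2 this mainly concerns RTM (up to 5 weekly sessions). A TF-CBT participant who uses most of the up to 18 weekly sessions already has week 6 and week 12 scores at discharge, so 4.2 has a reference.

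**Step 6: number of comparisons.** The between-follow-up rule applies to at most three intervals per participant: weeks 6–12, 12–20 and 20–52.

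**Step 7: after the change.** If 2.3 also counts a rise of at least 10 points since the previous follow-up, its PCL-5 triggers at follow-up equal those of 4.2 and the gap is empty.

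**The case against.** The strongest reply is that the previous therapy session can naturally mean the last one held, and nothing in 2.3 says this comparator lapses at discharge. That carries weight. A reader might reach for a starker case, such as baseline 50, week 12 = 20, week 20 = 60: a 40-point rise that is only 10 above baseline. On the last-session reading it is an adverse event whenever the last session scored 50 or less (60 − 50 = 10). To stay in the gap the participant would have to leave therapy at 51 or more and then fall at least 31 points by week 12. The large literal ranges should not be presented as the only reading. The gap shrinks on this reading but does not close, as Step 4 shows, and the protocol does not state the reading.

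A second reply is that the heading over 4.2 already makes the rise an adverse event, and that Appendix 4 lists relapse as an example. But the heading then disagrees with the definition, and Appendix 4 does not say whether it means symptom or substance relapse.

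Four stronger inferences are tempting, and the protocol does not support them.
- *Participants are left unprotected.* Under 2.2.1, "The named researcher will review all incoming follow up PCL-5 scores within 72 hrs of receipt", and 4.2 requires contact within six hours of the rise being noted.
- *The DMEC is not told.* Under 4.1.2 a rise during therapy "will be detected by the unblinded member of the research team who will inform the DMEC chair within 3 working days", and 4.2 has no such step. But by 1.4, "The research team will report any participant safety issues to the DMEC within 48 hrs of each fortnightly" meeting, which is at worst 14 + 2 = 16 days after the rise is noted. Wanting the shorter interval is a preference.
- *Events are under-counted in one arm.* The arms differ in session numbers, but nothing in the protocol shows how often gap cases would occur in either arm.
- *Progression is distorted.* Appendix 4 sets no adverse-event rate.

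The point about row 16 is also modest. Its source column lists the participant, and the follow-up PCL-5 is self-report in the same booklet.

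**Conclusion.** The mismatch is in the text and holds, as a minor point. A post-discharge rise of at least 10 points between follow-ups that stays under baseline plus 15 and under 80, with no hazardous alcohol or substance relapse, triggers 4.2 but is not an adverse event under 2.3. The mismatch runs one way: every follow-up score that meets a PCL-5 trigger in the literal 2.3 also meets 4.2.

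Its size depends on the reading of 2.3. Read literally, it spans rises of 10 to D + 14 points. With the last session as comparator, it is limited to participants whose previous follow-up was below their last-session score, and is empty otherwise. These are ranges of possible scores; the protocol gives no basis for saying how many participants would fall in them.

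The missing reference for 4.2 at week 6 applies only to participants discharged before then. The consequence is confined to the completeness of the adverse-event log. The scores stay in the outcome data, so the rises could be counted later.

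**What to change.** - In 2.3, add a further trigger: *or a rise of at least 10 points from the previous follow-up or, if there is none, from the last available PCL-5 score*.
- Use the same reference in 4.2, which also settles the week 6 case.
- In Appendix 5, row 16, name the follow-up PCL-5 as a source for the adverse events log.
- Optional: state in 4.2 whether the 3-working-day notice to the DMEC chair applies at follow-up.

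The cost is a few words in three places and no new data collection. The downside is more recorded adverse events, some in participants still below their baseline score. If the team does not want to record those, the alternative is to say in 2.3 that such rises are escalated but not logged as adverse events, and why.
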